## PROTOCOL SYNOPSIS

Title:	Peers and Technology for Adherence, Access, Accountability, and Analytics (PT4A) – A Qualitative Study
Grant Number:	1R56HL150036
Study Description:	
The overall objective of this project is to utilize the PRECEDE-PROCEED framework to conduct transdisciplinary, translational implementation research focused on improving medication adherence for hypertension control. The central hypothesis is that peer delivery of medications integrated with HIT (PT4A) will be effective in improving hypertension medication adherence, contributing to improved blood pressure among patients with uncontrolled hypertension in western Kenya. This application will focus on the critical formative components of the overall implementation research objective, and we propose the following specific aims:
 
Aim 1 will identify micro- and macro-level contextual factors that might influence the implementation of the PT4A strategy (individual, family, clinician, health system, and environment), using qualitative methods. Aim 2: We will then use a human-centered design approach to refine the PT4A intervention using the findings from Aim 1. Sub-Aim 2.1 will evaluate the intervention for acceptability and appropriateness by use of a survey tool with patients, peers, and clinical staff. In Sub-Aim 2.2, we will then conduct a pilot of the intervention and conduct a survey questionnaire with patients, peers, and clinical staff to evaluate feasibility. We will evaluate impact on systolic blood pressure, medication adherence, and fidelity of implementation. We will also create a retrospective comparator (control) group of CDM patients, through querying AMRS, matched by sex, age, location and initial blood pressure level. We will then use their recorded blood pressure over a comparable period of upto 1 year and to allow for comparison to the blood pressure changes observed in the patients enrolled in the PT4A program to help understand the magnitude and variance of the intervention effects.

Objectives*:	The overall objective of this proposal is to utilize transdisciplinary, translational implementation research, guided by the PRECEDE-PROCEED framework, to address the challenge of hypertension medication non-adherence in low-resource settings.

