Study Population:	
Approximately 146 individuals will participate in this study. The number is approximate because for focus group discussions, the number of participants can range from 6-10.
 
Aim 1:
 
 
• Focus group discussions (approximately 96 participants): Participants will be patients with hypertension who are currently enrolled in the AMPATH CDM program, and at least 18 years of age from the counties of Bungoma, Trans Nzoia, and Uasin Gishu in Western Kenya. Clinical staff in the AMPATH CDM program and community leaders from the counties will also participate. (12 total FGDs, 6-10 participants each)
 
• Key informant interviews (4 participants): Participants will be County Executive Committee representatives for health from the three Counties included in the study and the Ministry of Health head for non-communicable diseases (NCDs).
 
 
Aim 2:
 
 
• Human Centered Design Team (20 participants): Participants will be individuals representing the following stakeholder groups: research team members, clinicians, pharmacists, peers, patients with hypertension, representatives from the informatics team, and other relevant staff members involved in hypertension care
 
 
Aim 2.1:
 
 
• Use of Survey tools adapted from acceptability and appropriateness measures (39 participants):
 
• Participants will be patients (as described above), peer navigators, and clinical staff (as described above).
 
 
Aim 2.2:
 
 
• Pilot (up to 100 participants): Participants will be patients who are currently enrolled in the AMPATH CDM program, and at least 18 years of age from the counties of Bungoma, Trans Nzoia, and Uasin Gishu in Western Kenya.
 
• Retrospective comparator group: AMRS records of up to 100 patients who will serve as a control group matched by sex, age, location and initial blood pressure level
 

Phase* or Stage:	N/A
Description of Sites/Facilities Enrolling Participants:	AMPATH catchment area in three counties of western Kenya: Bungoma, Trans Nzoia, and Uasin Gishu.

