We will evaluate the impact of the pilot on absolute mean change in SBP and medication adherence from baseline to **up to 1 year**. The primary adherence outcome is the pill count adherence ratio, which is the proportion of prescribed doses taken over a 1-month time period, assessed at the end of the pilot. The primary implementation outcome is fidelity, measured as quantity and quality of intervention delivery as intended, comprised of three components: confirmed medication delivery documented by patient e-signature, peer completion of the HIT form, and quality of data entry into the HIT form.

We will also create a retrospective comparator group of CDM patients, by querying AMRS, matched by sex, age, location and by initial blood pressure level. We will use their recorded blood pressure over time and compare the 3, month, 6 month and 1 year change in blood pressure to those of the patients receiving the PT4A intervention to evaluate the magnitude and variance of the intervention effects.

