#### **Subaim 2.2: Conduct a pilot of the intervention and evaluate feasibility**

##### **Participants:**

Three health facilities will participate in the pilot (one from each county involved in the study). One peer delivery agent will be hired per facility and will be in close contact with clinicians, pharmacy staff, and patients at each health facility. The study will include all who are involved in the care for these patients and we target to enroll a total of **up to 100 patients** in this phase. **Ten patients per facility.**

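### The matched blood pressure comparison names change from baseline but states no baseline adjustment, no use of the matching in the analysis and no matching tolerance

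*Combined protocol and SAP*

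**What the plan says.** Section C, Sub Aim 2.2 first gives a within-pilot outcome: "We will evaluate the impact of the pilot on absolute mean change in SBP and medication adherence from baseline to" up to one year. It then adds a retrospective comparator group from AMRS, "matched by sex, age, location and by initial blood pressure level", and plans to "compare the 3, month, 6 month and 1 year change in blood pressure to those of the patients receiving the PT4A intervention". The stated purpose is "to evaluate the magnitude and variance of the intervention effects". The Protocol Synopsis (Study Description) describes the same contrast, recorded pressures that will "allow for comparison to the blood pressure changes observed in the patients enrolled in the PT4A program". Its Study Population entry gives up to 100 pilot patients and "AMRS records of up to 100 patients who will serve as a control group matched by sex, age, location and initial blood pressure level".

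Appendix A (Subaim 2.2, Outcomes and Analysis) repeats only the mean change in SBP and does not mention the comparator. Nowhere do the documents name a model, a baseline covariate, a paired or matched-set analysis, an interval method, a tolerance for matching on initial pressure, or a balance check. The comparator sentences say blood pressure; I read this as SBP because SBP is the pilot's stated blood pressure outcome.

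**The concern.** The design conditions on initial pressure by matching, but the stated contrast then subtracts initial pressure from follow-up pressure. Change from baseline treats follow-up as moving one-for-one with baseline. For readings months apart the slope is likely to be below 1, and two things follow.

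- If the two groups' changes are compared as independent samples, the standard error includes baseline variation that the matching has already removed from the group difference.
- If matching is loose, part of any leftover baseline gap appears as a treatment difference.

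This is the pilot's only controlled blood pressure estimate. Its size and spread are the purpose of the comparison, and a cluster randomised trial is planned to follow. An interval of the wrong width, or a centre that depends on an unstated tolerance, would carry forward.

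**Working it through.** **Inputs.**
- Group size: up to 100 each (Synopsis, Study Population); 1:1 matching assumed.
- Yardstick: the nearly 6 mmHg SBP reduction reported under Preliminary Data, an earlier pilot result and not a design assumption.
- SD of SBP: not given; 20 mmHg assumed at both times.
- Baseline to follow-up correlation r: not given; 0.3, 0.5 and 0.6 assumed. With equal SDs the slope equals r.
- The documents state no standard error, power or sample-size figure for this comparison, so there is nothing to reproduce.

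**Step 1. Two-sample change against baseline-adjusted follow-up, baselines not truncated.**
SE(change) = √(2 × 2 × 20² × (1 − r) / 100). SE(adjusted) = √(2 × 20² × (1 − r²) / 100).

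| r | SE change | SE adjusted | Excess width, √(2/(1 + r)) − 1 |
|---|---|---|---|
| 0.3 | √11.2 = 3.35 | √7.28 = 2.70 | 24% |
| 0.5 | √8.0 = 2.83 | √6.0 = 2.45 | 15% |
| 0.6 | √6.4 = 2.53 | √5.12 = 2.26 | 12% |

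The excess depends on r, not on the SD.

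**Step 2. Truncated baselines.** If pilot baselines are cut at an assumed 140 mmHg, baseline variance falls to a fraction v of 20² and the excess becomes √(1 + v(1 − slope)/(1 + slope)) − 1. With an assumed untruncated mean of 150, v is about 0.486, giving 12%, 8% and 6% at slopes 0.3, 0.5 and 0.6. A lower mean reduces it a little more, so the range is about 5 to 12%.

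**Step 3. Where the excess comes from.** A simulation used 100 pairs matched within ±5 mmHg, SD 20, no true effect and 1,500 runs per setting.

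| r | Actual SE: change / adjusted | Reported SE: two-sample / paired / adjusted | Coverage of two-sample 95% interval |
|---|---|---|---|
| 0.3 | 2.84 / 2.83 | 3.34 / 2.69 / 2.69 | 97.3% |
| 0.5 | 2.49 / 2.48 | 2.83 / 2.45 / 2.45 | 97.4% |

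After close matching the two estimates are equally precise. Only the two-sample standard error is too large.

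**Step 4. Residual baseline gap.** If PT4A patients start d mmHg above their matches and both groups share the same usual mean, the change contrast is off by (1 − slope) × d in favour of PT4A; if they start lower, it is off against PT4A. For d = 5: 0.7 × 5 = 3.5, 0.5 × 5 = 2.5 and 0.4 × 5 = 2.0 mmHg. Simulation at slopes 0.3 and 0.5 gave 3.50 and 2.48, with the adjusted contrast within 0.03 of zero.

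**Step 5. What adjustment leaves.** Suppose instead that pilot patients' usual pressure is stably D mmHg above the record pool's. With a common slope, the adjusted contrast is off by (1 − slope) × D against PT4A, and the change contrast by (1 − slope) × (D − d). For an assumed D = 3, the adjusted contrast is off by 2.1, 1.5 and 1.2 mmHg. With d = 1.5, the change contrast is off by about half that: 1.05, 0.75 and 0.6.

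**The case against.** The documents name a quantity, change in pressure, and not an estimator. Regressing change on group and initial SBP also compares change, and gives the same group coefficient as the model proposed below. A reader might infer that the plan has chosen an unadjusted, unpaired analysis. It has not; it is silent. Matching on initial pressure is itself partial control.

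A reader might also infer from Step 1 that adjustment is worth 54%, 33% or 25% more patients (2/(1 + r) − 1). That holds for unmatched groups. Step 3 shows that it does not hold for a closely matched design, where a paired analysis loses almost nothing. This stands, with one limit: pairing needs both members observed. The comparator pressures are routine records, and the milestones table itself anticipates incomplete data. If an assumed 30% of readings were missing independently per person, 0.7 × 0.7 × 100 = 49 complete pairs would remain. At r = 0.5 the paired SE is then √(2 × 400 × 0.75 / 49) = 3.50, against √(2 × 400 × 0.75 / 70) = 2.93 for the adjusted comparison.

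Nor can the direction of any leak be asserted. The consent section speaks of inviting patients with uncontrolled hypertension, which would suggest higher pilot baselines, but the inclusion criteria in Sub Aim 2.2 and Appendix A set no pressure threshold. Step 5 also stands: in a non-randomised comparison, adjustment is not always less biased than change. Finally, the named primary outcomes are pill count adherence and fidelity, so this is a supporting comparison.

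**Conclusion.** The point holds as a gap in the stated analysis with a conditional cost. If the comparison is run as a plain two-sample difference in change, its interval is about 12 to 24% wider than the adjusted one for r from 0.6 to 0.3, or about 5 to 12% wider with baselines cut at 140 mmHg. A paired analysis of complete, close pairs would avoid most of that.

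It would be too strong to say that the whole of any baseline gap counts as PT4A effect. Only the fraction (1 − slope) passes through, in either direction. Even so, 2.0 to 3.5 mmHg from a 5 mmHg gap is large beside a preliminary effect of nearly 6 mmHg, and with no tolerance stated the documents do not rule out such a gap.

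SD, correlation, tolerance, cut-off, missingness and pool difference are all assumptions, so the mmHg figures are illustrative. They also assume 100 per group. Appendix A (Subaim 2.2, Participants) gives both a total of up to 100 and "Ten patients per facility", which over three facilities is 30. At 30 per group and r = 0.5 the 95% half-widths would be 1.96 × √(2 × 400 / 30) = 10.1 mmHg for two-sample change and 1.96 × √(2 × 300 / 30) = 8.8 mmHg adjusted.

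**What to change.** In the Synopsis (Study Description) and Section C, Sub Aim 2.2:

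1. Replace the between-group comparison of change with one repeated-measures model. Regress SBP at each follow-up time on group, time, group by time, initial SBP, age, sex and location, accounting for matched sets and for repeated readings within a person. Report the adjusted difference with a 95% interval at each time, and keep mean change as a description.
2. State the tolerance for matching on initial pressure and whether matching is by pair or by frequency. Report baseline balance after matching.
3. Say that adjustment does not remove other confounding, including a stable difference in usual pressure between pilot patients and the record pool.

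Two conflicts must be reconciled first. Appendix A (Subaim 2.2, Methods) describes a 3-month pilot while Sub Aim 2.2 describes up to one year, and this decides which time points can be modelled. The ten-per-facility and up-to-100 figures decide the precision.

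The cost is a few sentences and a balance table. The model uses initial and follow-up pressures and matching factors that the plan already calls for, with no extra patients or visits.

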**Limitations and Alternative Strategies:** We may have trouble recruiting for the FGDs. To mitigate this, we will adhere to the principles of community engagement as described above, and hold sensitization sessions among potential participants. Given our success recruiting for similar research recently, we do not anticipate that this will be a significant issue. It is also possible to assess for these factors using a more quantitative approach. However, using the proposed type of qualitative methods, our team has successfully uncovered novel factors that have informed and impacted the implementation of previous strategies. It is possible that we will identify factors that are not aligned with the planned components of the PT4A strategy; in this scenario, we will incorporate those factors into the human-centered design approach described in Aim 2.

[figure not shown]
**Aim 2: Use a human-centered design approach to refine and adapt the PT4A strategy (to be implemented following completion of Aim 1 activities)**

We will pursue a participatory, iterative design process and assemble a human centered design (HCD) team consisting of individuals representing stakeholder groups: research team, clinicians, pharmacists, peers, and patients with hypertension, informatics staff, and other providers involved in hypertension care. The design process will involve three phases: brainstorming, conceptualization, and creation. During brainstorming, the facilitator will review relevant information on adherence to hypertension medications, findings from Aim 1, and the PT4A prototype core principles and characteristics. In the conceptualization phase, the team will evaluate advantages and disadvantages of ideas resulting from brainstorming, and arrive at consensus regarding importance, feasibility, and congruence to the PT4A strategy goals, in order to more concretely refine the strategy. In the creation phase, we will develop the refined PT4A strategy. Educational (for patients) and training (for peers) materials will be developed in English, Kiswahili, and other local languages as appropriate, using standard approaches to translation and back-translation.

Core components of the PT4A strategy will include a HIT component and a peer delivery component. Prototype characteristics of each are described as follows (Figure 3).

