## **Sub Aim 2.2: Conduct A Pilot of the Intervention and Evaluate Feasibility.**

We will also conduct a pilot of the strategy for up to **1-year** and conduct further FGDs to evaluate feasibility. We will select three pilot health facilities, one from each county. We will hire one peer delivery agent per facility, train them in core roles and responsibilities, and equip them with

tablets. Each peer will be stationed at a specific health facility and will be able to communicate directly with the clinicians, pharmacy staff, and patients. To maintain patient confidentiality, all research

Table 3: Acceptability, Appropriateness, and Feasibility of the PT4A Intervention	
	Outcomes
Acceptability	

• Satisfaction with the proposed intervention design

• Expressed interest or intention to participate

Appropriateness	

• Perceived relevance of intervention to address adherence

• Perceived fit within existing community and clinical infrastructure

Feasibility	

• Anticipated success of implementing intervention in this setting

• Perceived ease of implementing the intervention

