##### **Methods:**

The pilot study will be conducted over a 3-month period. Peers will be paid through the PT4A funds. After recruitment and hiring, they will be on-boarded through a week-long training that will cover: i) basic training on hypertension care, ii) use of the PT4A HIT tool to ensure proper documentation of medication pick-up, medication delivery, and peer-patient encounter documentation; iii) providing psychosocial support for hypertensive patients aimed at supporting medication adherence and promoting patient activation. Peers will use the AMRS system (peers will have access to a tablet with access to the HIT/AMRS system, and technological support will be provided by research and the Ampath informatics team) to request a prescription for a patient in the provider catchment. The AMRS system will send the prescription from the healthcare provider to the pharmacy that covers that network. The pharmacy will prepare individually sealed blister bags in individual single seal bags to lower pilferage. Once packaging is complete, the AMRS system will send a message to the peer with the name, date/time of delivery, location, type of drug, and quantity to ensure the right medication is picked up at the right time. The peer will pick up the prescription and then deliver the medication to the patient, confirming receipt by getting a signature from the patient on the HIT tool. The peer will then request the next installment of medications through the AMRS system, taking into account any pills not consumed (remaining in the blister pack). This cycle will repeat until the patient has to see the clinician again, where the clinician will provide a new prescription. During these deliveries, peers will leverage adherence data to support patients and address any barriers to medication adherence. The overall goal of this psychosocial support will be increasing patient activation.

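### The 1-year blood pressure contrast cannot include all PT4A patients, because study, participant and pilot durations share a 1-year ceiling and patients enter at clinic visits

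*Combined protocol and SAP*

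**What the plan says.** The Synopsis gives Study Duration and Participant Duration the same ceiling of one year. C. Approach, Sub Aim 2.2, says the team will "conduct a pilot of the strategy for up to 1-year and conduct further FGDs to evaluate feasibility". The impact outcome there is "absolute mean change in SBP and medication adherence from baseline to up to 1 year". The same section plans to "compare the 3, month, 6 month and 1 year change in blood pressure to those of the patients receiving the PT4A intervention", the comparators being retrospective AMRS patients matched on sex, age, location and initial blood pressure. For these controls the Synopsis refers to "recorded blood pressure over a comparable period of upto 1 year".

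Three other places bear on the time available:

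- Informed Consent and Assent describes Aim 2 patients being invited and enrolled at a routine clinic visit.
- The Milestones table puts the design process at M8, focus groups with patients, peers and clinical staff at M9, pilot implementation at M11 and pilot analysis at M12. The order is sequential: Aim 2 is "to be implemented following completion of Aim 1 activities", and Sub Aim 2.1 follows Aim 2.
- Appendix A, Subaim 2.2, Methods, states: "The pilot study will be conducted over a 3-month period".

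No section gives an enrolment window, a last-enrolment date, visit windows, a data cut-off or a rule for who contributes at each time. The nearest text is a Milestones entry promising a missing-data algorithm that is still to be developed.

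**The concern.** To observe every patient for one year, a study must run for one year plus the length of enrolment. Here study, participant and pilot share one ceiling, which leaves no room for enrolment. The 1-year contrast would then have no PT4A patients, or only the earliest to enter, set against historical controls whose records can in principle span a full year.

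The impact outcome has a related defect. A change measured to a ceiling has no fixed time point, so it averages patients with different lengths of time on PT4A. The comparable-period wording for the controls does not tie each control's follow-up to that of its matched patient.

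This comparison is the study's only one against a control group. Its stated purpose is to show the size and variance of the intervention effect, and a cluster randomised trial is planned next. A 1-year figure from a small, early-entering subset would be a poor basis for that planning.

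**Working it through.** The plan states no sample size, power or alpha for this comparison, so there is no figure to reproduce. The check is follow-up arithmetic.

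**Inputs**

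- W, months from first enrolment to close: 12 (Synopsis; Sub Aim 2.2), 3 (Appendix A; also end of M8 to end of M11), or 2 (end of M9 to end of M11).
- t, the comparison times: 3, 6 and 12 months (Sub Aim 2.2).
- A, the enrolment length: not stated. Assumed uniform over 3, 6 or 9 months, with no dropout.

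**Formula.** The share of patients who can have t months of follow-up is min(1, (W − t)/A), and 0 if W < t.

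**W = 12**

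| A (months) | 3 months | 6 months | 12 months | Month 11 counted as 1 year |
|---|---|---|---|---|
| 3 | 100% | 100% | 0% | 1/3 = 33% |
| 6 | 100% | 6/6 = 100% | 0% | 1/6 = 17% |
| 9 | 9/9 = 100% | 6/9 = 67% | 0% | 1/9 = 11% |

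The 0% means that only patients enrolled on the first day have a full 12 months. The month-11 column is an assumed visit window, since the plan defines none. With 100 patients it leaves about 33, 17 or 11. With 30 (Appendix A also says ten at each of three facilities) it leaves about 10, 5 or 3. The 6-month share falls below 100% only when (12 − 6)/A < 1, that is, when A > 6.

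**Unequal exposure.** If the last possible reading is used for an outcome measured to up to one year, time on PT4A runs from 12 − A to 12 months. That is 9 to 12, 6 to 12 or 3 to 12 months for A = 3, 6 or 9, with means (12 − A/2) of 10.5, 9 and 7.5 months.

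**W = 3 or 2.** With W = 3, only first-day enrolees reach 3 months, and nobody reaches 6 or 12. With W = 2, none of the three times is reachable.

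**Window needed.** For every patient to reach 1 year, W must be A + 12, which is 15, 18 or 21 months for A = 3, 6 or 9. No section provides this.

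**The case against.** A fair opponent would say that each duration is a ceiling, that no enrolment length is stated, and that the one-year pilot could mean exposure per patient rather than a calendar window. The staggered-entry premise also rests on a consent section that speaks of randomised patients and uncontrolled hypertension. Neither fits this non-randomised pilot or its eligibility criteria, so the text may belong to the planned trial. The named primary outcomes are pill count adherence and fidelity, not blood pressure.

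Much of this stands, and it limits the point. Several stronger readings are tempting but unsupported:

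- That no PT4A patient can reach 1 year. If the 12 months is the pilot window, first-day enrolees do, and a tolerant visit window admits more.
- That the patient sets shrink at every step. Timing alone leaves the 3- and 6-month sets identical unless enrolment exceeds 6 months.
- That early enrolees must be the most frequent attenders. This is plausible but not shown, and entry order may simply follow appointment dates.
- That the controls have complete data. AMRS readings are routine records, and Preliminary Data reports that only 24% of those due for a refill returned, so gaps are likely.
- That the plan will compute three separate means. It says only that changes will be compared.

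The objection does not remove the core. Recruiting up to 100 patients across three facilities on a single day is not realistic, whatever the status of the consent text. If the one year is exposure per patient, the study would have to run past its own stated ceiling. The comparable-period wording for controls helps only in part, because it sets a common maximum and not a matched length.

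**Conclusion.** The point holds for the 1-year contrast and for the outcome measured to up to one year. On the reading most generous to the plan, a 12-month pilot window, essentially only first-day enrolees have a 1-year reading. About 33%, 17% or 11% qualify if month 11 is accepted and enrolment takes 3, 6 or 9 months. These shares rest on assumed uniform enrolment and no dropout; dropout would lower them. Whether the early subset is biased depends on entry date being related to blood pressure change, which the documents neither show nor rule out.

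On the Milestones table or Appendix A, the position is worse: 6 months is also unreachable and 3 months is marginal. The documents contradict one another on pilot length, and that must be settled before any main comparison time can be chosen. Settling it at one year would still leave the 1-year problem. This should be corrected, but it does not touch the named primary outcomes.

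**What to change.** 1. Reconcile the pilot length across the Synopsis, Sub Aim 2.2, the Milestones table and Appendix A.
2. State the enrolment window, the last-enrolment date, the data cut-off and the visit window around each time.
3. Replace the up-to-one-year horizon with one fixed SBP time, the latest planned time that every enrolee can reach before close, and make it the main comparison with the AMRS group.
4. Limit each matched control's follow-up to the length available to its PT4A patient.
5. Report how many PT4A patients and controls contribute at 3, 6 and 12 months.
6. Drop the 1-year contrast, or label it as describing early enrolees only.

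A repeated-measures model using all readings, with group by time, is a reasonable option but not essential. It cannot supply 1-year data that were never collected.

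The cost is mainly protocol and analysis wording, with no new data collection. It does change the stated SBP horizon, and the 1-year result is downgraded or lost.
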